Фонд за науку
Републике Србије

Utility of plasma drug level monitoring and *CYP2C19* genotyping in dose personalization of escitalopram therapy

PsyCise_E

Principal Investigator: **Asst. [name] PhD**

Department of Physiology, Faculty of Pharmacy, University of Belgrade, Serbia

Document Date: 12th January 2022

Clinical trial protocol

Test groups:

PsyCise trial is designed to quantify changes in clinical outcomes in participants treated for depression using personalized antidepressant dosing regimen, based on therapeutic drug monitoring (TDM) and CYP2C19 genotyping; as compared to the standard, “one size fits all” dosing. In order to reach this goal, we have defined two test groups based on the TDM findings. Namely, all participants who enter the trial (Visit 0) will begin taking standard escitalopram dose of 10 mg/day for two weeks when their blood samples will be taken for the purpose of TDM, and based on their steady state escitalopram concentrations they will be allocated to one of two groups at week 4 of the trial (visit 1):

- 1) “Standard dose” group: Participants will be allocated to this group if their TDM results at week 2 show their steady state escitalopram plasma concentrations were inside “therapeutic window” (25-50 ng/ml). For these participants, initial standard escitalopram dose of 10 mg/day is estimated to be optimal so they will continue to receive the same dose until the end of the trial at week 8 (visit 2).
- 2) “Adjusted dose” group: If TDM results at week 2 suggest that participant taking standard dose is underdosed or overdosed, given participant is allocated to this group. New, personalized dosing regimen will be produced for this participants based on steady state escitalopram plasma concentrations measured at week 2, and they will receive personalized escitalopram dose from week 4 (visit 1) until the end of the trial at week 8 (visit 2).

Course of the trial:

Week 0

Initial Visit (Visit 0 – V0)

- Participant will be enrolled at this point if inclusion criteria are met.
- Escitalopram monotherapy for Major Depressive Disorder in previously untreated patient will be initiated at standard dose of 10 mg/day.
- Outcomes measured:
 1. General and socio-demographic information
 2. Clinical questionnaires
 3. Anthropometric measurements
 4. Cardiological assessment
 5. Serum samples for biochemical analyses
 6. Buffy coat samples for DNA extraction and *CYP2C19* genotyping*

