(*Sample is not time dependent, it can be taken at any visit)

Week 2

Mid-Visit (Vk)

- Escitalopram plasma concentrations reach steady state.
- Plasma sample taken for the purpose of TDM and group allocation.

- Percentages of participants who are underdosed and overdosed will be measured and used to confirm previous findings [Jukić 2018]

Week 4

Visit 1 (V1)

- Participants are allocated to the “Standard dose” or “Adjusted dose” group
- Independent clinician prescribes new dosing regimen to the participants in “Adjusted dose” group, and informs patients in “Standard dose” group to continue taking the same standard escitalopram dose.
- Clinician who usually monitors given patient is unaware of the group patient is allocated to, or the dose prescribed to a patient at Visit 1.
- Outcomes measured:
 1. Clinical questionnaires
 2. Anthropometric measurements
 3. Cardiological assessment
 4. Serum samples for biochemical analyses
 5. Plasma samples to reconfirm TDM findings in VK

Week 8

Visit 2 (V2)

- Final visit of the trial and the end of the follow-up.
- Outcomes measured:
 1. Clinical questionnaires
 2. Anthropometric measurements
 3. Cardiological assessment
 4. Serum samples for biochemical analyses
 5. Plasma samples to reconfirm TDM findings in VK and V1 for Standard dosing group, and to determine whether personalized dose is optimal for the patients in Personalized dosing group.

If needed, alternative course will be used:

Week 0

Initial visit + Mid-visit (V0+k)

- Participant on the stable (longer than 2 weeks) monotherapy of Major Depressive Disorder with standard dose of escitalopram (10 mg/day) will be enrolled if other inclusion criteria are met.
- Outcomes measured:
 1. General and socio-demographic information
 2. Clinical questionnaires
 3. Anthropometric measurements
 4. Cardiological assessment
 5. Serum samples for biochemical analyses
 6. Plasma sample for the purpose of TDM and group allocation.
 7. Buffy coat samples for DNA extraction and *CYP2C19* genotyping*

(*Sample is not time dependent, it can be taken at any visit)

Week 2

Visit 1 (V1) – *Identical to the standard protocol*

- Participants are allocated to the “Standard dosing” or “Personalized dosing” group
- Independent clinician prescribes new dosing regimen to the participants in “Personalized dosing” group, and informs patients in “Standard dosing” group to continue taking the same standard escitalopram dose.

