- Clinician who usually monitors given patient is unaware of the group patient is allocated to, or the dose prescribed to a patient at Visit 1.
- Outcomes measured:
 1. Clinical questionnaires
 2. Anthropometric measurements
 3. Cardiological assessment
 4. Serum samples for biochemical analyses
 5. Plasma samples to reconfirm TDM findings in V_k

Week 6

Visit 2 (V2) – *Identical to the standard protocol*

- Final visit of the trial and the end of the follow-up.
- Outcomes measured:
 1. Clinical questionnaires
 2. Anthropometric measurements
 3. Cardiological assessment
 4. Serum samples for biochemical analyses
 5. Plasma samples to reconfirm TDM findings in V_k and V1 for Standard dosing group, and to determine whether personalized dose is optimal for the patients in Personalized dosing group.

Hypotheses:

- 1) More than one quarter of participants will be overdosed or underdosed under standard escitalopram dosing regimen (10 mg/day), as determined by TDM data 2 weeks after the beginning of the therapy.
- 2) Participants with escitalopram steady state plasma concentration outside the therapeutic window (“Adjusted dose” group) will experience reduced efficacy and more severe side effects of escitalopram therapy before dose personalization (at V1) compared to the participants with escitalopram levels within therapeutic window (“Standard dose” group) at standard dosing.
- 3) Participants with escitalopram steady state plasma concentration outside the therapeutic window (“Adjusted dose” group) will show improved efficacy and less severe side effects of escitalopram therapy after dose personalization (at V2) as compared to before (at V1), and will reach clinical outcomes comparable to the “Standard dose” group (at V2).

- 4) Decisions on whether to use personalized or standard dosing, and how to adjust personalized dose based on TDM data could have been determined before the beginning of the treatment using predictive model which, besides other predictors also includes *CYP2C19* genotyping data.

Statistical Analysis Plan

Primary outcomes:

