Other primary outcome we will use to quantify changes in clinical outcomes between test groups will be severity of the treatment side effects measured using clinician reported UKU (*Udvalg for Kliniske Undersogelser*) side effect rating scale. UKU scale rates 48 potential adverse reactions with intensity score ranging from 0 to 3 where score 3 signifies maximal intensity and score 0 signifies absence of the adverse reaction. Adverse drug reaction intensity scores for all 48 adverse reactions monitored with UKU scale will be measured at weeks 4 (V1) and 8 (V2) after the initiation of the escitalopram therapy. Due to large number of comparisons, significance measures will be adjusted using False Discovery Rate (FDR) correction. Absolute values of all 48 Adverse reaction scores will be compared between test groups and between two time points using mixed model analysis of covariance (Mixed ANCOVA) where variables will be assigned as follows:

1. Dependent variable: Adverse drug reaction score for the given adverse reaction measured by UKU scale
2. Independent variable - Fixed factor: Test group (Personalized vs Standard dosing)
3. Independent variable - Repeated measurements: Visit (Visit 1 vs Visit 2)
4. Covariables: Age, Sex (Male=0, Female=1), Smoking status (0=Non-smoker, 1=Smoker), Alcohol consumption (0=No, 1=Yes), Coffee consumption (0=No, 1=Yes), Use of psychoactive substances (0=No, 1=Yes), Metabolic syndrome (0=No, 1=Yes), Creatinine clearance, AST/ALT ratio.

Positive outcome: interaction between group and visit is significant ($\alpha=0.05$)

Alternatively, proportions of patients with intensity score greater than 0 (UKU scale intensity score >0 signifies the presence of the given adverse reaction) will be compared between the groups for all 48 adverse effect monitored with UKU scale at two time points: 4 weeks after the enrolment (V1) and 8 weeks after the enrolment (V2). Due to large number of comparisons, significance measures will be adjusted using False Discovery Rate (FDR) correction. Proportion of individuals in two test groups affected with the given adverse reaction will be compared using binary logistic regression analysis separately for visit V1 and visit V2 as follows:

1. Dependent variable: Frequency of the individuals affected with the given adverse drug reaction measured by UKU scale

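### A patient who stops escitalopram after the week-2 sample and misses V1 leaves the side-effect comparison of hypothesis 2, and the stopping is counted in no analysis

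*Combined protocol and SAP*

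**What the plan says.** The order of events in the standard course is spread over several sections.

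- **Test groups:** the group depends on the week-2 concentration but takes effect later: "based on their steady state escitalopram concentrations they will be allocated to one of two groups at week 4 of the trial (visit 1".
- **Course of the trial, Week 2 (Vk):** after the remark on steady state, the only procedure is "Plasma sample taken for the purpose of TDM and group allocation". No questionnaire or side-effect scale is listed.
- **Course of the trial, Week 4 (V1):** "Participants are allocated to the “Standard dose” or “Adjusted dose” group". Clinical questionnaires are first repeated here.
- **SAP, Primary outcomes (UKU):** the 48 item scores "will be measured at weeks 4 (V1) and 8 (V2) after the initiation of the escitalopram therapy". They are analysed by mixed ANCOVA. Alternatively, the proportions scoring above 0 "will be compared using binary logistic regression analysis separately for visit V1 and visit V2".
- **SAP, Primary outcomes (HAM-D):** rated at V0, V1 and V2.
- **Hypotheses, number 2:** patients outside the window "will experience reduced efficacy and more severe side effects of escitalopram therapy before dose personalization (at V1". Hypothesis 3 then measures improvement from V1 to V2.

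No section defines an analysis set, deals with withdrawal or missing data, provides for recording side effects between visits, or lists stopping for an adverse reaction as an outcome.

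**The concern.** Hypothesis 2 predicts worse side effects outside the window during the first four weeks. Some patients with a troublesome reaction may stop before the week-4 rating. Under the schedule as written, those who do not return contribute nothing to the comparison meant to detect such reactions, and the stopping itself, a direct sign of poor tolerability, is not tabulated. The V1 starting point for hypothesis 3 is selected in the same way.

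This is not only a matter of missing V2 scores. Here V1 is missing as well, and the patient has not been formally placed in a group. A rating not taken at the time of stopping cannot be recovered afterwards.

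**Working it through.** The documents state no sample size, dropout rate or side-effect frequency, so there is no planned figure to reproduce. The check is a trace, followed by arithmetic on assumed rates.

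**1. Trace of a standard-course patient who stops at week 3 and misses V1**

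- Week-2 level: available. It can enter the count outside the window and the regression on the Vk concentration (both under Secondary outcomes).
- Formal allocation: none, because it is a V1 step.
- UKU: none.
- HAM-D: baseline only.
- Stopping and its reason: in no analysis.

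**2. Effect on the V1 logistic regression**

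Let a share x of a group have a reaction and a share r of those affected stop before V1. The proportion seen at V1 is x(1−r)/(1−xr). The unaffected remain at 1−x, so the odds seen are x(1−r)/(1−x). If r is the same in both groups, (1−r) cancels from the odds ratio. Taking 40% and 20% purely to show the algebra:

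- all patients: (0.40/0.60)/(0.20/0.80) = 2.67
- r = 50%: 25.0% and 11.1%, so (0.250/0.750)/(0.111/0.889) = 2.67

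The odds ratio moves only if r differs between the groups.

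**3. Effect with the expected make-up of the Adjusted group**

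Secondary outcomes expects about 40% of patients below and 10% above the window. The Adjusted group is therefore 0.40/0.50 = 80% below and 0.10/0.50 = 20% above. The reaction and stopping rates below are assumptions. Differences are Adjusted minus Standard, from unrounded values.

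| Reaction rate: below / within / above | Affected who stop: below and within / above | Adjusted vs Standard at V1 | Difference (points) | Odds ratio |
|---|---|---|---|---|
| 20 / 20 / 50% | none | 26.0% vs 20.0% | +6.0 | 1.41 |
| same | 10% / 10% | 24.0% vs 18.4% | +5.7 | 1.41 |
| same | 10% / 30% | 22.4% vs 18.4% | +4.1 | 1.29 |
| same | 10% / 50% | 20.8% vs 18.4% | +2.4 | 1.17 |
| 15 / 20 / 50% | none | 22.0% vs 20.0% | +2.0 | 1.13 |
| same | 10% / 30% | 18.6% vs 18.4% | +0.2 | 1.01 |
| same | 10% / 50% | 16.8% vs 18.4% | −1.5 | 0.90 |

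Third row in full:

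- Adjusted, affected and still present: 0.8×0.20×0.9 + 0.2×0.50×0.7 = 0.214
- Adjusted, all still present: 0.8×0.98 + 0.2×0.85 = 0.954
- Adjusted proportion: 0.214/0.954 = 22.4%
- Standard proportion: 0.18/0.98 = 18.4%
- Odds ratio: (0.214/0.74)/(0.18/0.80) = 1.29

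In that row 4.6% of the Adjusted group and 2.0% of the Standard group are lost before V1. Counting them as affected, in their week-2 class, restores the all-patient row.

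**4. Effect on mean UKU scores**

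The mixed ANCOVA compares mean item scores from 0 to 3. If stopping rises with severity, the highest scores leave first. At the extreme, if every patient scoring 3 stopped, no score above 2 would be seen in either group, and an Adjusted excess confined to score 3 would vanish. A difference in means is then reduced even under one stopping rule for both groups. This describes the usual case, in which most patients do not have the given reaction.

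**The case against.** The strongest reply has four parts.

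- **The patient is not lost to classification.** The week-2 level fixes the class; only its communication waits for V1. This stands, and it is why the repair is easy. A reader might infer that such a patient is dropped from the whole trial. That is too strong: the week-2 level can still count in two analyses.
- **A patient who stops may still attend V1.** The documents do not exclude this. Such a patient could be allocated and rated, but off drug, and no rule covers that case. The point is therefore limited to those who do not attend. It is also limited to the standard course: in the alternative course the V0 HAM-D is already on treatment, and the questionnaires at V0+k are not itemised.
- **Bias toward no difference is not shown.** A reader might infer that the V1 comparison must be diluted, for example that 40% versus 20% shrinks from 20 points to 13.9 when half of those affected stop. The documents do not support this. The planned analysis is logistic, and its odds ratio stays at 2.67. Nor does a 20-point gap fit the expected group: if below-window patients had the within-window rate of 20%, the above-window rate would have to be (0.40 − 0.8×0.20)/0.20 = 120%. This objection stands in full for the odds ratio under equal stopping. It does not dispose of mean scores, or of unequal stopping, which more severe reactions outside the window could plausibly produce.
- **It is a special case of having no missing-data rule.** Partly so, since a patient lost before V1 will usually lack V2 too. But a general rule for missing scores would neither collect the rating at stopping nor count the stopping.

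**Conclusion.** The gap is certain for the standard course. A patient who stops after Vk and misses V1 has no UKU rating and no on-treatment HAM-D, and the stopping enters no analysis. The V1 side-effect comparison and the V1 starting level for hypothesis 3 rest on those who reached V1.

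The consequence is conditional. Differences in mean UKU score are reduced if stopping rises with severity. The V1 odds ratio is biased only if the share of affected patients who stop differs by group. Neither size nor direction follows from the documents. Under the assumed rates the change runs from negligible (6.0 to 5.7 points) to a reversal of a small difference (+2.0 to −1.5). Because about 80% of the Adjusted group is expected to be below the window, even heavy stopping above it acts on a minority.

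This is a worthwhile, inexpensive improvement. It does not show that hypothesis 2 will give a wrong answer.

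**What to change.** Amend the protocol and SAP briefly, before further patients pass through this interval.

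- **(a) Class by the sample.** For analysis, class every patient with a Vk (or V0+k) sample by that level, whether or not V1 is attended. Allocation as communicated to patients stays at V1.
- **(b) Rate at stopping.** When a patient stops before V1, complete the existing UKU form then and record the date and reason. Use it as the V1 UKU value in the side-effect analysis of hypothesis 2, with a sensitivity analysis without it. If HAM-D is also rated then, use it only in a sensitivity analysis, because the shorter treatment would otherwise mix into the efficacy comparison.
- **(c) Report the stopping.** Tabulate stopping for an adverse reaction by below, within and above the window as a side-effect outcome. In the V1 proportion analysis, count such a patient as affected only on the UKU item or items that led to stopping. Counting all 48 would create false events.

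The cost is small: existing forms, no new instrument, and no change to any dose or treatment rule. The drawback is that these few ratings are taken before week 4. Patients who stop before the week-2 sample have no TDM class and are not recovered by this change.

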To assess the efficacy of the escitalopram therapy under different dosing regimens we will use 21-item Hamilton rating scale for depression (HAM-D). Depression severity score will be measured at baseline (V0), at week 4 (V1) and week 8 (V2) after the beginning of the treatment. Since there is the need to compare depression severity scores between two test groups as well as between the visits V1 and V2, mixed analysis of covariance (Mixed ANCOVA) will be used if all assumptions associated with ANCOVA are met. Variables will be assigned as follows:

1. Dependent variable: Depression severity score measured by HAM-D scale
2. Independent variable - Fixed factor: Test group (Personalized vs Standard dosing)
3. Independent variable - Repeated measurements: Visit (Visit 1 vs Visit 2)
4. Covariates: Baseline HAM-D score (V0), Childhood trauma questionnaire score at V0, Age, Sex (Male=0, Female=1), Smoking status (0=Non-smoker, 1=Smoker), Alcohol consumption (0=No, 1=Yes), Metabolic syndrome diagnosed using siMS score [Soldatović 2016] (0=No, Yes)

Positive outcome: interaction between group and visit is significant ($\alpha=0.05$)

Besides using absolute HAM-D scores, we will also compare relative changes in HAM-D scores between V1 and V2 visits as another way to express the potential differences in therapy efficacy between the two test groups. If all needed assumptions are met, statistical test used will be analysis of covariance (ANCOVA) with variables assigned as follows:

1. Dependent variable: Relative change in HAM-D score between visits V1 and V2 calculated by formula:

$$\frac{HAMD_{V1} - HAMD_{V2}}{HAMD_{V1}}$$

2. Independent variable: Test group (Personalized dosing vs Standard dosing)
3. Covariables: Baseline HAM-D score (V0), Childhood trauma questionnaire score at V0, Age, Sex (Male=0, Female=1), Smoking status (0=Non-smoker, 1=Smoker), Alcohol consumption (0=No, 1=Yes), Metabolic syndrome (0=No, Yes)

Positive outcome: Test group is a significant factor ($\alpha=0.05$)

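### Patients who enter by the alternative course have an on-drug V0 and later visits in treatment time, but the SAP neither tabulates nor models entry course in its non-randomised groups

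*Combined protocol and SAP*

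**What the plan says.** **Standard course.** The Test groups section says that "all participants who enter the trial (Visit 0) will begin taking standard escitalopram dose of 10 mg/day for two weeks". The Initial Visit entry says that escitalopram monotherapy "in previously untreated patient will be initiated at standard dose of 10 mg/day". V0 is therefore before treatment, and V1 and V2 are at weeks 4 and 8 of both treatment and enrolment.

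**Alternative course.** This is conditional on need. The protocol gives no criterion for need and no cap on numbers. The entry rule is "Participant on the stable (longer than 2 weeks) monotherapy of Major Depressive Disorder with standard dose of escitalopram (10 mg/day) will be enrolled", subject to the other inclusion criteria, and the visible text sets no upper limit on prior treatment. The initial visit and the TDM mid-visit are merged into one on-drug visit. V1 is headed Week 2 and V2 Week 6, and both are labelled "Identical to the standard protocol".

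**SAP.** HAM-D is "measured at baseline (V0), at week 4 (V1) and week 8 (V2) after the beginning of the treatment". UKU scores are timed at 4 and 8 weeks from start of therapy, UKU proportions at 4 and 8 weeks from enrolment, and HAM-A at weeks 4 and 8 of treatment. The V0 value is a covariate for HAM-D, HAM-A, cortisol and QT. The primary HAM-D criterion is a significant group-by-visit interaction at 0.05. Entry course and time on drug appear in no covariate list, table, subset or sensitivity analysis. The two groups are defined by plasma concentration, not by randomisation.

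**The concern.** V0 means two different things: an untreated score in one course and an on-drug score in the other. V1 and V2 also sit at different points on the response curve, because new starters are still improving while long-treated patients may have levelled off. If one plasma-level group holds more alternative-course patients, or patients treated for longer, that difference can look like a group effect.

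Two comparisons are exposed. One is the primary group-by-visit interaction. The other is any V0-adjusted comparison of groups at V1 or V2. Hypotheses 2 and 3 rely on the latter, although the SAP does not make it a positive-outcome test.

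**Working it through.** **1. Visit times.** Let w be the weeks of prior treatment, with w > 2.

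| | V0 | V1 | V2 | V1 to V2 |
|---|---|---|---|---|
| Standard, weeks of treatment and of enrolment | 0 | 4 | 8 | 4 |
| Alternative, weeks of enrolment | 0 | 2 | 6 | 4 |
| Alternative, weeks of treatment | w | w+2 | w+6 | 4 |
| Alternative, w = 12 | 12 | 14 | 18 | 4 |

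The alternative visits match neither SAP definition. Weeks 4 and 8 of treatment would need w = 2 exactly, which the entry rule excludes.

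**2. Bias formula.** With no true group effect and no V0-by-visit term, interaction bias = (difference between groups in alternative-course share) x (difference between courses in mean V1-V2 improvement). With complete data, a V0 term without a visit interaction cannot alter the V1-V2 contrast.

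**3. Assumed inputs.** The documents give no sample size, SD, response curve or course shares, so there is no plan figure to reproduce. Assumed: mean HAM-D at treatment week t of 8.8 + 13.2 x exp(-t/4), that is 22 at start falling to 40% of start; SD at start 4; visit error SD 3.5; patient deviation SD 2 on drug; 50 or 100 per group.

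- Standard-course V1-V2 improvement: 13.66 - 10.59 = 3.07.
- Alternative course, w = 12: 9.20 - 8.95 = 0.25.
- Difference: 2.82. A 14-point gap gives 0.14 x 2.82 = 0.39, and a 30-point gap gives 0.30 x 2.82 = 0.85.

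**4. Simulated interaction bias, w = 12** (HAM-D points; type I error where available). The SAP does not say which V0 reading applies.

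| Share, Standard/Adjusted | No V0-by-visit term | V0-by-visit term |
|---|---|---|
| 30/30 | noise (at most 0.05); 3.9-5.5% | same |
| 32/28 | 0.10-0.11 | 0.03 |
| 36/22 | 0.37-0.41; about 6-8% | 0.09-0.14; 5-6% |
| 50/20 | 0.80-0.88; 11-21% | 0.23-0.30; about 6% |

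With more alternative-course patients in the Standard dose group, the Adjusted dose group appears to improve more. The sign reverses if the mix is reversed. With w = 2.1 and a 30-point gap, interaction bias is at most 0.10 and error about 5%. For the relative-change ANCOVA, bias is at most 0.03 and error 4-6%, for gaps up to 30 points.

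**5. V0-adjusted contrast at V1, w = 2.1.** Mean V0 is 22 untreated and 8.8 + 13.2 x exp(-0.525) = 16.6 on drug. Mean V1 is almost the same in both courses (13.66 and 13.54), so adjusting for V0 overcorrects. Bias is 0.42-0.49 points for a 30-point gap and 0.20-0.26 for gaps of 14 to 17 points.

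**6. Equal shares, unequal duration.** With 30% in each group, but prior treatment of 2-4 weeks in one and 10-26 in the other, interaction bias is 0.69-0.73 without V0-by-visit and 0.46-0.49 with it. Course terms do not remove this.

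**7. One inferred route to a 14-point gap.** The SAP expects 40% + 10% = 50% out of window. Suppose such patients are half as likely to be still on an unchanged 10 mg/day when recruited, and 30% of all patients enter by the alternative course.

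- Out-of-window share of alternative entrants: 0.25/0.75 = 1/3.
- Alternative share in the Standard dose group: 0.20/0.55 = 36.4%.
- Alternative share in the Adjusted dose group: 0.10/0.45 = 22.2%.
- Gap: 14.1 points.

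Selection could also run the other way.

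**8. After the fix.** In the unequal-share scenarios, course terms leave interaction bias of at most 0.04 with error 4.0-5.6%. Restricting to the standard course gives at most 0.04 and 4.4-5.5%. Effects on UKU, HAM-A, cortisol and QT were not quantified.

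**The case against.** The strongest case is that this is a fallback that may enrol few or nobody, that no document shows an imbalance, and that the primary test compares two visits four weeks apart in both courses. At the 14-point gap from the inferred route, type I error hardly moves if V0 interacts with visit. The 12-week scenario implies a mean entry HAM-D of about 9.5 (8.8 + 13.2 x exp(-3)), and the remaining inclusion criteria, which might exclude such patients, are not visible. All of this stands, and it limits the point to a conditional one. It does not remove it: the SAP would not reveal an imbalance if one arose.

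Four stronger readings are tempting, and the documents do not support them.

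- A reader might infer that the SAP prescribes pooling. It does not say so. Pooling is a reasonable inference from its silence.
- A reader might infer that the primary result is already biased. That needs both a difference between groups in course or duration and a different V1-V2 change, and neither is shown. A purely chance gap in shares does not inflate the error rate.
- A reader might take the label on the alternative V1 and V2 as a claim about timing. It stands under explicit Week 2 and Week 6 headings and above matching procedure lists, so it more naturally refers to content.
- A reader might think Hypothesis 1, set "as determined by TDM data 2 weeks after the beginning of the therapy", is undermined. This is mainly a timing mismatch, since the protocol says steady state is reached by week 2 and these patients are past it.

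In the other direction, an equal course mix is not a full safeguard, as step 6 shows.

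**Conclusion.** The point holds in conditional form. The mismatch in visit timing and in the meaning of V0 follows from the text alone. Bias in the primary HAM-D test arises only if course mix or prior duration differs between the plasma-level groups and V1-V2 change differs by course or duration.

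Its size cannot be derived from the documents. Under the assumed inputs it runs from negligible to about 0.8 HAM-D points, the upper end needing a 30-point gap, 12 weeks' prior treatment and no V0-by-visit term. V0-adjusted contrasts at V1 can be off by about 0.5 points even with short prior treatment, at a 30-point gap. The change is worth making because it is cheap. Confidence is medium, and the point is minor if few or no patients use the alternative course.

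**What to change.** 1. Reconcile the Test groups section, the alternative course and the SAP on treatment status at V0 and on visit timing.
2. Record entry course and weeks of prior treatment, and tabulate both by group.
3. Add course and course-by-visit to the primary HAM-D mixed model and to the other mixed models, including the UKU mixed ANCOVA. Add course to the ANCOVAs of relative HAM-D change and CGI change. State whether V0 interacts with visit.
4. Use course-by-V0 only for V0-adjusted contrasts at V1 or V2, and only if enough patients enter by the alternative course. It does not change the interaction test in the unequal-share scenarios. Leave the UKU logistic models as they are unless event counts allow a course term.
5. Pre-specify the primary HAM-D analysis in standard-course participants alone as a sensitivity analysis. This also removes bias from unequal prior duration. An optional second one adds log prior duration, coded within the alternative course only (zero for the standard course, alongside the course term). In simulation, a log-duration term left at most 0.04 points of bias.

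**Cost.** SAP wording, one extra recorded item and a few model terms. The interaction standard error rises by at most about 5%. In the standard-course-only analysis standard errors are about 20% larger if 30% enter by the alternative course (assumed; 1/sqrt(0.70) = 1.20).

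### Hypothesis 3 claims comparable outcomes at V2, but no V2 contrast or comparability criterion is prespecified for HAM-D; both success rules concern change from V1 to V2.

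*Combined protocol and SAP*

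**What the plan says.** Under Hypotheses, item 2 expects the Adjusted group to start behind: its participants "will experience reduced efficacy and more severe side effects of escitalopram therapy before dose personalization (at V1"). Item 3 then makes two claims. The Adjusted group improves from V1 to V2, and its outcomes end up level with those of the Standard group: "at V2) as compared to before (at V1), and will reach clinical outcomes comparable to the" Standard dose group. The documents do not define what counts as comparable.

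The SAP, Primary outcomes, sets two HAM-D rules:

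- Mixed ANCOVA on the HAM-D score, with group, visit (V1, V2) and covariates: "Positive outcome: interaction between group and visit is significant", at alpha 0.05.
- ANCOVA on relative change. The outcome is "Dependent variable: Relative change in HAM-D score between visits V1 and V2 calculated by formula" (V1 − V2)/V1, and the rule is "Positive outcome: Test group is a significant factor", at alpha 0.05.

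Neither rule requires a direction, names a group contrast at V2, or gives a margin. The only between-group test made at V2 by itself is for UKU side effects, which are "compared using binary logistic regression analysis separately for visit V1 and visit V2 as follows". That is a significance test without a margin, and it does not cover HAM-D. The documents state no sample size and no HAM-D standard deviation.

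**The concern.** Being comparable at V2 is a statement about the size of the group difference at V2. A difference in change answers another question: whether the gap between the groups moved. A gap can shrink and still be large, so a significant result under either rule is consistent with an Adjusted group that remains worse.

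The mismatch also runs the other way. If the two groups have the same HAM-D mean at both visits, they are comparable at V2, yet there is no interaction to find. Because no direction is required, a widening gap meets the interaction rule as readily as a narrowing one.

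At stake is the second half of hypothesis 3. As written, the HAM-D analysis could be carried out in full and leave that clause neither supported nor refuted. With no criterion fixed in advance, nothing guards against reading a non-significant V2 difference as comparability.

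**Working it through.** There is no figure in the plan to reproduce. The first step is algebra and needs no assumptions; the rest is illustration.

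**1. What the interaction measures.** With two groups and two visits, and gap = Adjusted minus Standard (a higher HAM-D score is worse):

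interaction = (gap at V1) − (gap at V2)

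- Gap 6 falling to 3: 6 − 3 = 3.
- Gap 3 falling to 0: 3 − 0 = 3.
- Gap 3 rising to 6: 3 − 6 = −3, which a two-sided test detects equally often.
- Gap 0 at both visits: 0, so the rule is met in about 5% of trials, the alpha level.

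Only the second and fourth cases end with equal groups.

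**2. The relative-change rule.** Take Standard 14 to 11 and Adjusted 20 to 14 (assumed means). Relative change is 3/14 = 21% against 6/20 = 30%, which favours the Adjusted group, while it remains 14 − 11 = 3 points worse at V2.

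**3. How often this could happen.** Assumptions, none from the documents: HAM-D SD 7 (range 6 to 8), V1–V2 correlation 0.6, 25, 50 or 100 per group, no covariates, true gap 6 at V1 and 3 at V2. Equal groups are assumed because Secondary outcomes expects about 40% of patients below and 10% above the therapeutic window, so about half outside it.

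- SD of change = 7 × √(2 × (1 − 0.6)) = 6.26.
- SE of the interaction at 50 per group = 6.26 × √(2/50) = 1.25; 3/1.25 = 2.40. Power by non-central t is 66%.
- SE of the V2 difference at 50 per group = 7 × √(2/50) = 1.40; 95% CI half-width = 1.984 × 1.40 = 2.8.

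| Per group | Interaction significant (SD 6–8) | True 3-point V2 deficit non-significant (SD 6–8) | V2 95% CI half-width, SD 7 |
|---|---|---|---|
| 25 | 38% (31–49%) | 68% (59–75%) | 4.0 |
| 50 | 66% (55–79%) | 44% (30–54%) | 2.8 |
| 100 | 92% (84–98%) | 15% (6–25%) | 1.95 |

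If the correlation also varies from 0.5 to 0.7, the interaction figures run from 46% to 89% at 50 per group and from 75% to over 99% at 100.

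**4. Both results in one trial.** Simulating the same scenario at SD 7, the interaction is significant and the Adjusted group is also significantly worse at V2 in about 7%, a little over 30% and about 77% of trials with 25, 50 and 100 per group.

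**5. Effect of covariates.** If the planned covariates together correlate 0.5 with the V2 score (assumed), the residual SD is 7 × √(1 − 0.25) = 6.06. Non-significance of a 3-point V2 deficit then falls from 44% to 31% at 50 per group and from 15% to 6% at 100.

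**6. What a margin would demand.** For non-inferiority with a true V2 difference of 0, one-sided 0.025 and 80% power, n per group = 2 × SD² × (1.96 + 0.842)² / margin². For a purely illustrative margin of 3 points, SD 6 gives 63 and SD 8 gives 112. A 2-point margin gives 142 to 252, and a 4-point margin 36 to 63.

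**The case against.** The strongest reply is that the V2 difference is already in the model. The mixed ANCOVA has group, visit and their interaction, so the adjusted difference at V2 is a linear combination of its terms. The SAP also introduces the model with "Since there is the need to compare depression severity scores between two test groups as well as between the visits V1 and V2". This stands: it would be wrong to say that the planned model cannot estimate the V2 difference. What is missing is the naming of that contrast and a criterion for it.

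A reader might infer that the plan will declare comparability from a significant interaction, or from a non-significant V2 difference. The documents say neither. The interaction is labelled a positive outcome for HAM-D, and it is a valid test of differential change. Nor do they present comparability as the trial's headline claim. It is the last clause of one of four hypotheses, and the aim under Test groups is to quantify changes in clinical outcomes.

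*Comparable* may also have been meant informally. A V2 difference with its confidence interval, cautiously described, would then be enough. That is a fair alternative, provided no conclusion of comparability is drawn from it.

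Finally, the percentages rest wholly on assumed values. At 25 per group the interaction rule is met in only 38% of trials, and at 50 per group a single trial would usually not show both a significant interaction and a significant V2 deficit. The size is therefore uncertain; the algebra is not.

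**Conclusion.** The point holds for HAM-D: one clause of hypothesis 3 has no prespecified contrast or criterion, and the two success rules cannot stand in for one. That follows from the definition of the interaction. How often the rules would be met with a deficit remaining depends on the assumed SD, correlation, gaps and group sizes. The illustrative range is wide, from about 31% (25 per group, SD 8) to 98% (100 per group, SD 6) at correlation 0.6.

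This should be corrected, but it does not invalidate the interaction as a test of differential change. A stronger reading would be that meeting a V2 margin shows personalization brought out-of-window patients to the level of the others. The documents do not support that either: Test groups allocates participants by plasma concentration, not at random, so closeness at V2 would show similarity between the groups and not its cause.

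**What to change.** In the SAP, under the HAM-D mixed ANCOVA:

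- Prespecify and report the covariate-adjusted Adjusted-minus-Standard difference in HAM-D at V2 with its 95% CI.
- State whether *comparable* means non-inferior or equivalent. Conclude it only if the relevant CI limit (the upper one for non-inferiority, both for equivalence) lies within a margin in HAM-D points that is justified and fixed before data are examined.
- If no margin can be justified, report the difference and CI and draw no conclusion of comparability.
- State that a significant interaction, in the direction favouring the Adjusted group, shows differential change only, and that a non-significant V2 difference is not evidence of comparability.
- Word any result as similarity between groups at V2, not as an effect proven to be due to personalization.

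The cost is SAP wording and one contrast from a model already planned; no new data are needed. The downside is that the sponsor must commit to a margin, and the claim may not be reached in a small sample.
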